8.1.4 Intermittent Assessments

- Exhaled breath sampling, daily post-onset of infection in Recipients and in Donors
- Venous whole blood (~10 mL) collection
- Nasal swab for viral detection and nasal swabs and saliva for research tests at PI discretion.

8.1.5 Assessment within 48 hrs from Influenza Infection (Recipients)

Approximately 48 hrs (window 36-60 hrs) from virologic-confirmation of influenza infection (e.g., BioFire positive test), a blood volume of ~10 mL will be collected for the following safety labs: white blood cells (WBC), absolute lymphocyte count (ALC), hemoglobin (Hgb), platelets (PLT), alanine transaminase (ALT), and creatinine (Cr). The ALC is a variable under the Modified Jackson score. (see Appendix C for Score).

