6.9 Discharge Criteria

Subject discharge is planned at approximately 14 days (for Recipient participants) or 2-5 days (for Donor participants) after entry. To be eligible for discharge home, the participant must meet the following criteria: no greater than moderate severity influenza signs or symptoms (Appendix A) and are clinically stable during their stay. In addition, the participant must attest that they feel well enough to provide their own self-care. Otherwise, Recipients will be discharged as described in escalation of care (Section 6.8). Recipients must be at least 2 days post the end of their last exposure event to be eligible for discharge. We may discharge Recipients with a home influenza test to ensure that we do not miss late onset, long latency, influenza infection. However, recipients who have contracted the flu but do not wish to be a donor may be discharged earlier. In this case, they must meet the discharge criteria described above for discharge home. All other instances will be handled as described in Section 6.8.

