7 SAFETY AND OTHER ASSESSMENTS

7.1 Procedures to be Followed in the Event of Abnormal Laboratory Test Values or Abnormal Clinical Findings

The site PI or designated clinician licensed to make medical diagnoses will record, assess, and follow abnormal laboratory test values and abnormal clinical findings to collect adverse events (AEs) that are observed or reported during the study.

Signs, symptoms, and laboratory findings that are part of mild to moderate influenza disease, including mild or moderate fever and lymphopenia from the time of onset of illness through 7 days post-onset, will not be considered AEs. These signs, symptoms, and laboratory findings (mild and moderate) include the following: runny nose, stuffy nose, sneezing, sore throat, headache, cough, malaise (tiredness), body aches, chills, feverish, shortness of breath, earache, fever, and lymphopenia. Mild to moderate fever and mild to moderate lymphopenia is defined in Appendix A. Influenza infection-related symptoms that are deemed by the investigator to be severe, in addition to severe fever and severe lymphopenia as defined in Appendix A, will be considered as AEs.

Safety will be assessed by the frequency and severity of:

- Study intervention-related serious adverse events occurring from the time of the first exposure event until 2 months post-discharge from the hotel quarantine facility).
- Clinical safety laboratory adverse events occurring from the time of the first exposure event through discharge from the hotel quarantine facility. Parameters to be evaluated include white blood cells (WBCs), absolute lymphocyte count, hemoglobin, platelets, alanine transaminase (ALT), and creatinine (Cr).
- Adverse Events – non-serious adverse events occurring from the time of the first exposure through approximately 28 days post-last-exposure. See below for how adverse events are defined.

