8.1.6 Ad hoc Assessments

At the request of the study physician, ad hoc assessments may be performed to facilitate the close monitoring and management of influenza illness. These assessments must be documented with signed orders and accompanied by a doctor's note which provides clinical assessment and judgement.

- 12-lead electrocardiogram may be performed for complaints of chest pain, pressure or tightness, feelings of heart fluttering, or sustained tachycardia.
- Vital signs measurements may be changed in frequency (e.g., increased frequency) for the management of influenza illness
- Clinical laboratory assessments which might include serum chemistry, hematology, coagulation, cardiac enzymes, and urinalysis (listing not exhaustive of possible lab assessments which could be performed)

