8.1.7 Discharge/exit from a CHIVITT cohort

- Vital signs (including SpO₂, HR, RR, BP, and oral temperature) will be obtained, if not completed within the past 12 hours
- A targeted physical examination may be performed, as directed by the signs and symptoms, medications, and vital signs assessment. An absence of concurrent signs or symptoms and abnormalities in vital signs will not require a physical examination.
- Performance of a combined influenza and SARS-CoV-2 test (e.g., BioFire Respiratory Virus panel), if not done within the past 12 hours

- Collection of a respiratory sample for viral quantitation and saliva sample, if not done within the past 12 hours
- Venous whole blood (~10 mL) collection, if not done within past 48 hours
- Review follow-up procedures, discharge medications (if any), and indications for seeking additional medical care.

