17 APPENDIX D: SCHEDULE OF EVENTS

Recipients Participating in a CHIVITT Cohort

Inform of upcoming CHIVITT, ~1 wk prior
 Sign Recipient CHIVITT Consent Form
 Vital signs (SpO₂, HR, RR BP, temp)
 Targeted physical exam
 Nasal Swab, resp virus panel
 Nasal Swab, viral quantification
 Saliva Sample, viral quantification
 Nasal Wash, ~5-10 mL
 Point of care urine pregnancy for FOCBP
 Research Blood, ~10 mL
 Clinical Safety Lab Blood, ~10 mL
 Modified Jackson Score, twice daily
 FLU-PRO survey⁷, once daily
Exposure Events
 Exhaled Breath Sampling
 12-lead electrocardiogram
 Influenza Therapy (anti-viral)
 Adverse Event Reporting

CHIVITT – approx. 14 days on Quarantine Research Unit (w/in 48h) (w/in 72h)								Outpt Clinic Follow-Up ~1 month	Phone Call Follow-Up ~2 months
Pre-Adm	Admission	Daily*	Intermittent or Additional	upon influenza infection	(as requested) Ad Hoc	Discharge, ~Day 14			
X									
	X								
	X	X ¹			X	X ³			
	X	X				X			
	X	X ²	X			X ³			
	X	X ²	X			X ³			
	X	X ²	X			X ³			
	X						X		
	X								
	X		X			X ⁴	X		
				X ⁵	X ⁶				
		X							
		X				X9			
			X						
			X						
				X8					
	X	X	X	X	X	X	X	X	X

* – Daily including Day 1 unless completed as part of admission procedures.

1 – routine daily vital signs are to be performed twice daily (morning and afternoon), except once a day if the Recipient has been observed on the unit for more than two days and has not been exposed to a Donor.

2 – routine daily swabs and saliva may not be necessary prior to first exposure to a Donor and after the first two days of negative tests.

3 – to be performed/collected if not done within the past 12 hours

4 – to be collected if not done within the past 48 hours

5 – these clinical safety labs include: WBC, ALC, Hgb, PLT, ALT, and Cr

6 – these clinical safety labs are to be determined by the requesting clinician; may include: chemistry, hematology, coagulation, cardiac enzymes, and urinalysis

7 – the FLU-PRO survey is completed by the participant

8- Unless consenting to continue in the CHIVITT as a Donor

9 – the FLU-PRO survey won't be administered at discharge if the discharge occurs before 3pm, as the survey becomes available at 3pm.

Donors Participating in a CHIVITT Cohort

Identification of potential influenza case
 Lab-confirmation influenza infection, w/in 48h
 $F \geq 100.2^{\circ}\text{F}$ AND cough or sore throat, w/in 48h
 Sign Donor CHIVITT Informed Consent Form
 Vital signs (SpO₂, HR, RR BP, temp)
 Targeted physical exam

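### The only scheduled Recipient safety panel falls due 36-60 h after virologic confirmation, yet infected Recipients may leave before then and the laboratory safety window closes at discharge

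*Protocol*

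**What the plan says.** **The panel.** Protocol section 8.1.5 times it "Approximately 48 hrs (window 36-60 hrs) from virologic-confirmation of influenza infection" and states that "a blood volume of ~10 mL will be collected for the following safety labs": WBC, ALC, Hgb, PLT, ALT and Cr. The Recipient table in Appendix D has two safety-laboratory entries. One is triggered by infection, with the footnote "these clinical safety labs include: WBC, ALC, Hgb, PLT, ALT, and Cr". The other is ad hoc, which section 8.1.6 describes as "Clinical laboratory assessments which might include serum chemistry, hematology, coagulation, cardiac enzymes, and urinalysis" at the study physician's request.

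**Leaving the unit.** Section 6.9 sets a general floor: "Recipients must be at least 2 days post the end of their last exposure event to be eligible for discharge". It then adds that "recipients who have contracted the flu but do not wish to be a donor may be discharged earlier". Section 6.4 likewise lets a Recipient who has become a countable case and does not wish to continue be discharged. The section 6.9 conditions are symptom severity, clinical stability and ability to self-care. No minimum time after confirmation is given, and the panel is not a condition. Section 2.5.1 describes a longer stay, about three days of isolation and observation after last exposure.

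**Other blood draws.** At discharge, section 8.1.7 lists "Venous whole blood (~10 mL) collection, if not done within past 48 hours". Appendix D classes this draw, and the one at the 1-month visit, as research blood.

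**What is counted.** One of the safety measures in section 7.1 is "Clinical safety laboratory adverse events occurring from the time of the first exposure event through discharge from the hotel quarantine facility".

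**The concern.** The panel is tied to the time of confirmation, while discharge is tied to the last exposure or to the participant's wish to leave. Nothing links the two. If a Recipient leaves before the window opens, the plan offers no scheduled occasion to draw the panel: the next visit is 3-5 weeks after discharge and carries no safety laboratory tests. If a site recalled the participant anyway, the result would fall outside the laboratory window in 7.1.

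Section 7.1 names these six parameters as a safety measure and treats severe lymphopenia as an adverse event. Section 6.11 has Grade 3 and higher laboratory results related to influenza reviewed monthly. The missing panels would not be a random subset of infected Recipients. They would come from people who decline Donor status and go home, and from those infected at the last exposures. A laboratory event rate would then describe mainly the infected Recipients who stayed.

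**Working it through.** The protocol gives no figure of its own to reproduce here. The check is a timing comparison.

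**Inputs from the protocol**
- Panel window: 36 to 60 h after confirmation (8.1.5).
- Earliest general discharge: 48 h after the end of the last exposure event (6.9); about 72 h of observation in 2.5.1.
- Earlier exit for infected Recipients: allowed, with no minimum (6.4, 6.9).
- Incubation: 24 to 48 h (2.5.1).
- Exposure: for example 4 days at 15 h per day, which may be spread over up to 9 or 10 days (6.1).
- Influenza test at discharge unless done in the past 12 h (8.1.7).

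**Step 1: early leavers (no assumption needed).** A Recipient who leaves less than 36 h after confirmation leaves before the window opens, whenever the infection occurred.

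**Step 2: limit for everyone else.** Let T be the end of the last exposure, C the time of confirmation and D the hours from T to discharge. The window opens before exit only if C + 36 ≤ T + D, that is C ≤ T + (D − 36).
- D = 48: C must be no later than T + 12 h.
- D = 72: C must be no later than T + 36 h.

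**Step 3: infection at the very end of the last exposure.** Assume that the test turns positive when incubation ends. Then C lies between T + 24 and T + 48 h. The panel falls due between T + 60 h (24 + 36) and T + 108 h (48 + 60). All of this is later than T + 48 h. A first positive on a discharge test at T + 48 h makes the panel due at T + 84 to T + 108 h, which is 36-60 h after exit.

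**Step 4: share of all infections.** Further assumptions: four consecutive 15-hour days, equal risk across exposure hours, incubation uniform over 24-48 h, and everyone leaving exactly at D. Let u, uniform on 0-15 h, be the time from infection to the end of that day's exposure, and let I be the incubation time.

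*D = 48 h (missed if C > T + 12)*
- Last day: C = T − u + I, so missed if I > 12 + u. The panel is reachable only when u > 12 and I < 12 + u. That probability is ∫₁₂¹⁵ (u − 12) du / (24 × 15) = 4.5/360 = 0.0125. Missed: 0.9875.
- Day before: C = T − 24 − u + I, so missed if I > 36 + u. Probability ∫₀¹² (12 − u) du / (24 × 15) = 72/360 = 0.20.
- Two earlier days: none missed.
- Overall: (0.9875 + 0.20 + 0 + 0)/4 = 0.297, about 30%.

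*D = 72 h (missed if C > T + 36)*
- Last day: missed if I > 36 + u, probability 0.20.
- Earlier days: none missed.
- Overall: 0.20/4 = 0.05, about 5%.

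**Sensitivity to spacing.** If the last two exposure days have at least one free day between them, the second-last day contributes nothing. The 48 h figure becomes 0.9875/4 = 0.247, about 25%, and the 72 h figure stays at 5%.

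These shares exclude the early leavers of step 1, whose frequency the protocol does not give.

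**The case against.** The strongest reply is that the protocol does not say the panel is skipped. Section 8.1.5 states that the blood will be collected and does not limit this to people still on the unit. Section 8.1.6 lets the physician order laboratory tests at any time, including before exit. A reader might infer that these Recipients get no panel at all. The text does not go that far; it supports only that they have no scheduled occasion for it.

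A reader might also infer that the panel is always missed for infections on the last exposure day. Step 4 shows a small exception even at the 48 h floor (1.25% of last-day infections), and at 72 h, 80% of last-day infections reach the window before exit. The two days in 6.9 are a floor, and planned discharge is at about 14 days.

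Nor does all safety reporting stop at discharge. The next item in 7.1 collects non-serious adverse events to about 28 days after last exposure, and the section 7.2 definition of an adverse event includes abnormal laboratory findings. Section 6.6 follows symptoms to resolution, by telephone if need be. Other text suggests that many infected Recipients would remain: section 2.5.1 asks for breath samples for up to four days after onset or laboratory evidence of infection, and Appendix D places the infection-triggered columns inside the quarantine stay.

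Finally, 8.1.5 calls ALC a variable of the Modified Jackson score, so one might infer damage to the symptomatic part of the primary outcome. The form in Appendix C contains only symptom items, so that cannot be shown.

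These points limit the size of the problem but do not close the gap. Ad hoc tests are optional and need not be these six. Open adverse event reporting does not schedule a blood test. Placing the panel inside the stay does not help a person whom 6.4 and 6.9 allow to leave.

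**Conclusion.** The concern holds as a scheduling gap in a secondary safety measure. The only scheduled Recipient safety panel can fall due after a permitted discharge, no later visit provides it, and the clinical safety laboratory window in 7.1 has by then closed. The loss is selective: early leavers and late infections.

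Under the assumptions in step 4, the size is about 30% of infections at the 48 h floor in 6.9 and about 5% at the roughly 72 h stay in 2.5.1, plus early leavers. The sixfold range comes mostly from the two sections giving different stays after last exposure. The contradiction itself rests on none of these figures. It follows from 6.4, 6.9, 7.1, 8.1.5 and Appendix D read together. No effect on randomisation, power or the primary comparison is shown.

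**What to change.** Reconcile sections 2.5.1, 6.4, 6.9, 7.1, 8.1.5, 8.1.7 and Appendix D so that the panel is obtainable for every virologically confirmed Recipient. One way that uses an existing draw is to run the same six assays on the discharge venipuncture whenever the panel has not yet been drawn. The exemption for blood taken in the past 48 hours should not remove that draw in such cases. Record hours from confirmation so that early panels can be identified. Word the 7.1 laboratory window so that panel results arriving after discharge are counted.

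The two descriptions of the stay after last exposure (2.5.1 and 6.9) also need to agree. Which is right is for the investigators; no discharge or treatment rule is proposed here.

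The cost is a protocol and schedule amendment and an extra tube, at a draw already planned, for some of the infected Recipients. The drawback is that some panels would be taken earlier than 36 h after confirmation and would be less sensitive to abnormalities that develop later. A positive result first known after exit would still need separate provision.

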8.1.6 Ad hoc Assessments

At the request of the study physician, ad hoc assessments may be performed to facilitate the close monitoring and management of influenza illness. These assessments must be documented with signed orders and accompanied by a doctor's note which provides clinical assessment and judgement.

- 12-lead electrocardiogram may be performed for complaints of chest pain, pressure or tightness, feelings of heart fluttering, or sustained tachycardia.
- Vital signs measurements may be changed in frequency (e.g., increased frequency) for the management of influenza illness
- Clinical laboratory assessments which might include serum chemistry, hematology, coagulation, cardiac enzymes, and urinalysis (listing not exhaustive of possible lab assessments which could be performed)

8.1.7 Discharge/exit from a CHIVITT cohort

- Vital signs (including SpO₂, HR, RR, BP, and oral temperature) will be obtained, if not completed within the past 12 hours
- A targeted physical examination may be performed, as directed by the signs and symptoms, medications, and vital signs assessment. An absence of concurrent signs or symptoms and abnormalities in vital signs will not require a physical examination.
- Performance of a combined influenza and SARS-CoV-2 test (e.g., BioFire Respiratory Virus panel), if not done within the past 12 hours

- Collection of a respiratory sample for viral quantitation and saliva sample, if not done within the past 12 hours
- Venous whole blood (~10 mL) collection, if not done within past 48 hours
- Review follow-up procedures, discharge medications (if any), and indications for seeking additional medical care.

8.1.8 Outpatient Clinic Follow-up Visit (~1 month from CHIVITT)

Each subject who participated in a CHIVITT cohort will be contacted approximately 4 weeks (allowable window is 3-5 weeks) from their discharge from a CHIVITT cohort. The participant will be asked whether they have fully recovered from their influenza illness (if any) and whether there were any interim unscheduled medical visits. Venous whole blood (~10 mL) will be collected. Nasal wash specimen (~5-10 mL) will be collected. The participant will be afforded the ability to ask questions or raise concerns and to be provided the answers.

8.1.9 Phone call follow-up (~2 months from CHIVITT)

Each subject who participated in a CHIVITT cohort will be contact approximately 2 months (allowable window is 7-10 weeks) from their discharge from a CHIVITT cohort. The participant will be asked whether they have fully recovered from their influenza illness and whether there were any interim unscheduled medical visits. The participant will be afforded the ability to ask questions or raise concerns and to be provided the answers.

8.2 Research Laboratory Evaluations

HAI and FRNT Assays

The ability of antibodies to inhibit the interaction of hemagglutinin (HA) protein on the surface of influenza virus with sialic acids on the surface of red blood cells (RBCs) will be examined by hemagglutinin inhibition (HAI) assay performed on serum samples from study participants at the specified collection timepoints. The readout will be the ability of antibodies to inhibit hemagglutination, HAI titers. For H3N2 viruses that have no HA activity, serum antibody will be titred using a focus reduction neutralization test (FRNT) in which the ability of the serum to inhibit the formation of infectious foci in cell culture will be measured. The HAI and FRNT assays are to be performed with deidentified specimens at a collaborating lab ([name], Icahn School of Medicine at Mount Sinai, New York, NY). The virus strain-specific HAI or FRNT titer will be considered the primary method for determining a participant's immunity.

Potential Antibody Assays if funding is available

A brief listing of some of the potential additional antibody assays which may be performed on serum and/or nasal wash specimen includes the following:

- Microneutralization (MN) assay, measures the ability of antibodies to prevent cytopathologic effects in cell cultures infected with influenza viruses.
- Neuraminidase inhibition (NI) assay, measure antibodies that block the enzymatic activity of the neuraminidase protein (NA), a surface glycoprotein which cleaves sialic acid residues.
- Enzyme-linked immunosorbent assay (ELISA), measures binding antibodies against full-length HA, HA-stalk, NA, and other influenza antigens.

- Influenza virus protein microarray, an approach which can measure the “landscape” of serum antibodies by measuring the binding against hundreds of HA and NA proteins simultaneously and spanning multiple virus subtypes and strains.
- Antibody-dependent cellular cytotoxicity (ADCC) assay, functional antibody assay.

8.3 Secondary research use of stored specimens

Subjects will be asked to consent to the storage and secondary research use of leftover residual specimens. If they choose to not provide permission for leftover specimens for secondary research use, they will not be eligible for the study. However, a subject has the right to withdraw from secondary research at any time and will be instructed that they must submit this decision in writing to the principal investigator.

The secondary research use of the banked samples and data will require a separate study protocol with IRB approval before the use of the specimens. These residual samples will be stored with a barcode for an indefinite period of time at the CVD or the University of Maryland (College Park). The linking information (to PHI) will be maintained separately in a secured and locked location to which only authorized study staff members have access. Subjects will be notified that their residual samples (e.g., serum and nasal specimens) may be used for possible use in secondary research. Subjects will be informed that they cannot take part in this study if they do not agree to allow for the identifiable (coded) samples and data to be used for secondary research. Possible use in other research studies may include but is not limited to non-traditional immune assay development, assessing innate immune factors, cytokines, and other virologic evaluations. These residual samples will be stored indefinitely at a central clinical storage facility and may be shared with investigators at the participating site and with other investigators at other institutions. No genetic tests will be performed on samples. These specimens are not intended for any genetic studies or the creation of cell lines or commercialized products. These specimens would be used in laboratory-based assays to try to answer questions related to influenza or other respiratory viruses or vaccine-induced immune responses. Each sample will be encoded (labeled) only with a barcode and a unique tracking number to protect subject confidentiality.

